## **Purpose of the Study**

The study objective is to determine the feasibility and acceptability of a patient-centered, culturally-sensitive intervention addressing barriers to IP3 adherence identified by Non-Hispanic Black women. We hypothesize that the intervention is both feasible (ie. target enrollment reached and 95% of all intervention components delivered) and acceptable (over 80% of participants give the intervention top rating in their exit interview).

## **Background & Significance**

Preterm birth (PTB), delivery prior to 37 weeks gestation, is the leading cause of neonatal mortality and morbidity resulting in life-long medical complications such as blindness, chronic lung disease and intellectual disabilities. In 2019, the US PTB rate increased for the fourth consecutive year reaching 10 percent. Additionally, dramatic racial disparities persist such that the PTB rate is 49% higher in non-1 Hispanic black (NHB) women. Preterm birth (PTB) stems from multiple etiologies including medically indicated PTB and spontaneous PTB. Patients with a history of preterm birth seen in the Duke Prematurity Prevention Program are provided an Individualized Prematurity Prevention Plan (IP3). The IP3 is a targeted care plan that incorporates components tailored to a patient's individual risk factors for preterm birth such as life-style modifications (i.e. weight gain, nutrition recommendation, stress management), supplemental progesterone, serial cervix length screening, cerclage or low dose aspirin.

Adherence is a key component of success of the IP3. Given both the increasing PTB rate and persistent racial disparities, it is imperative to develop patient-oriented, culturally-sensitive interventions that improve the clinical encounter and increase IP3 adherence in NHB women. The current intervention was developed by a group of stakeholders and is grounded in qualitative data from NHB women about barriers and facilitators to supplemental progesterone for preterm birth prevention. The current proposal will test the intervention via a pilot randomized controlled trial comparing our intervention to an active control.

## **Design & Procedures**

Once consented, patients will complete an intake via a red-cap data base. The intake will include confirmation of basic demographics gleaned from the HER (e.g. age, self-described race, obstetrical history) and review of the participant's IP3. We will use redcap to randomize participants to the intervention or an active control.

The intervention arm includes:

1. A narrated powerpoint presentation describing the logistical details and medical rationale for components of the IP3. Participants will view the chapters of the presentation that are relevant to their specific IP3. There are a total of 4 possible chapters (lifestyle modifications, cervix length screening/cerclage, progesterone therapy, low dose aspirin). Each chapter of the presentation is ~ 10 – 15 min in length. Each chapter also includes a 4- 5 questions pre-test and the same questions are delivered as a post-test after the presentation.

2. Print materials including a letter explaining the importance of prenatal care for preterm birth prevention to employers. The letter will be given to the research participant and NOT directly to the employer. She will decide if and when the letter is provided. The letter, as with all aspects of the project, is optional for her to use. We will record which patients say they would like to use it and ask if patients actually used it and found it helpful during the exit interview.
3. Text messages sent weekly to encourage the patient to continue with their IP3 and provide basic pregnancy information
4. Formal letter of encouragement from provider at 28 weeks gestation

The active control arm includes:

1. A narrated powerpoint with general information about the Duke Prematurity Prevention Program
2. Text messages sent approximately weekly with general pregnancy information (e.g. Tylenol is most often safe in pregnancy)

For the subset of patients that have low dose aspirin or vaginal progesterone as part of their IP3 (whether they are in the control or the intervention arm), they will get an additional weekly text to gauge medication compliance.

Measures:

1. Demographic data – Via EHR review and intake interview we will collect basic demographic data (e.g. e.g. age, self-described race, obstetrical history) and review the participant's IP3
2. IP3 Knowledge: We will assess the participant's knowledge about the medical and logistical details of the components of their IP3. In the intervention group, knowledge will be assessed via a brief pre-test/post-test prior to each chapter of the narrated powerpoint. In the active control group knowledge will be assessed via the same questions that correspond to the pretest of the chapters that correspond to their IP3, however there will be a single assessment rather than a pre and post-test.
3. Pregnancy-Specific Anxiety (PSA): The PSA is a validated 13-item tool used to assess anxiety specific to pregnancy this tool has been correlated with preterm birth outcome. We will administer the PSA at intake and 28 weeks.
4. Interpersonal Processes of Care (IPC): The IPC is an 18-question questionnaire that asks participants about their experience with receiving care within a specific clinic (in this case the Duke Perinatal Durham Clinic).

5. Maternal Social Support Scale (MSSS): The MSSS is a six-question scale that quantifies a pregnant women's social support as low, medium or adequate. We will administer the MSSS at intake, 28 weeks gestation and postpartum

6. IP3 Adherence Data: We will gather data on adherence to the IP3 based on both participant report and EHR chart review.

7. Delivery outcomes: We will gather delivery outcome data (e.g. gestational age at delivery, birth weight, NICU admission, length of hospital stay) based on patient report and EHR chart review

### **Selection of Subjects**

We will recruit up to 60 pregnant women from the Duke Perinatal Clinics with the following inclusion criteria: self-described non-Hispanic Black race, history of prior preterm delivery (before 37 weeks gestation), current singleton gestation, with an IP3 documented. We will exclude women with anomalous fetuses, age below 18 or are non-English speaking.

The study staff will approach the subject and provide information regarding the study. If the patient is interested in participating, then study staff will obtain informed consent at that time. The patient can take as much time to decide about participation and the study team will come up with a plan with the patient to follow up on a decision to participate. Voluntariness will be emphasized. Patients will also be told that they were identified as being eligible because their medical chart indicated they have a history of a prior preterm birth.

For those patients who choose to 'opt out,' to prevent unwelcome emails, phone calls, or other contacts from those other than a patient's clinician, researchers/study teams must check the opt out status for each patient who may be eligible for their study and exclude those not wishing to be contacted.

### **Data Analysis & Statistical Considerations**

The proposed study is a feasibility and acceptability pilot study. We will measure:

Feasibility by:

- target enrollment reached
- 95% of all intervention components delivered

Acceptability will be measured by an exit interview which includes:

- quantitative assessment of the adherence to intervention components
- qualitative feedback about how the intervention should be changed
- participants overall rating of the intervention over 80% of participants give the intervention top rating in their exit interview.

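### Chapter adherence is to be taken from the exit interview, although the chapter post-tests already record it at the time and for women who are never interviewed

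*Combined protocol and SAP*

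**What the plan says.** Data Analysis & Statistical Considerations states: "Acceptability will be measured by an exit interview which includes" three items. The first is "quantitative assessment of the adherence to intervention components". The others are qualitative feedback on how to change the intervention, and the overall rating, whose target is that "over 80% of participants give the intervention top rating in their exit interview". The adherence item has no definition by component, no denominator, no threshold and no source other than the interview. Feasibility is judged separately, by reaching target enrolment and by "95% of all intervention components delivered".

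Design & Procedures describes four intervention components:

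- **Narrated presentation.** There are up to four chapters, and a woman views those relevant to her IP3. "Each chapter also includes a 4- 5 questions pre-test and the same questions are delivered as a post-test after the presentation".
- **Print materials, including an employer letter.** The wish to use it is recorded. Actual use and helpfulness are asked at exit.
- **Texts.** "Text messages sent weekly to encourage the patient to continue with their IP3 and provide basic pregnancy information".
- **Provider letter** at 28 weeks.

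The IP3 Knowledge item under Measures lists the chapter tests as planned data. The IP3 Adherence and Delivery outcomes items each combine participant report with chart review.

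**The concern.** Feasibility and acceptability are the objective of this pilot, and uptake of the components is one of the few things it sets out to measure. For the presentation, the plan collects a record chapter by chapter and then, as written, does not use it for the adherence figure. Two things are at stake.

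First, a woman's account at the end of the study of which chapters she completed may be wrong, and nothing in the plan checks it. A pilot needs to know which chapters were not taken up before a larger trial is designed.

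Second, a woman who gives no exit interview has no adherence value at all, although her chapter tests may be on file. Women who are lost before the interview may well be those who engaged least, so their absence is unlikely to be neutral.

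The plan also departs here from its own practice. For IP3 adherence and delivery outcomes it pairs self-report with a record; for adherence to its own intervention it names self-report alone.

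**Working it through.** The plan gives no adherence rate, recall accuracy or interview wording, so there is no stated figure to reproduce. The check has three parts.

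**1. Which components have a record that bears on uptake?**

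| Component | Record described in the plan | What it shows |
|---|---|---|
| Chapters | Pre-test and post-test for each relevant chapter | That the end of the chapter was reached: uptake |
| Weekly encouragement texts | Described only as sent; no log, receipt or reply | At most delivery |
| Provider letter | Timed at 28 weeks | Delivery |
| Employer letter | Wish to use it is recorded; use is asked at exit | Intention from the record; use from the woman only |

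The additional weekly compliance text and the chart review concern the IP3 itself, not the intervention components. Only the chapters have a planned record of uptake.

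**2. Which way could self-report err?**

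Let p be true uptake, Se the chance that a woman who completed a component says so, and 1 − Sp the chance that one who did not says she did. Then

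reported uptake = p × Se + (1 − p) × (1 − Sp).

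It exceeds p only if (1 − p)(1 − Sp) > p(1 − Se). All values below are assumptions.

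| p | Se | Sp | Reported uptake | Error (points) |
|---|---|---|---|---|
| 0.60 | 1.0 | 0.5 | 0.600 + 0.200 = 0.80 | +20 |
| 0.60 | 0.9 | 0.9 | 0.540 + 0.040 = 0.58 | −2 |
| 0.80 | 1.0 | 0.5 | 0.800 + 0.100 = 0.90 | +10 |
| 0.80 | 0.9 | 0.5 | 0.720 + 0.100 = 0.82 | +2 |
| 0.80 | 0.8 | 0.8 | 0.640 + 0.040 = 0.68 | −12 |
| 0.95 | 1.0 | 0.5 | 0.950 + 0.025 = 0.975 | +2.5 |
| 0.95 | 0.9 | 0.9 | 0.855 + 0.005 = 0.86 | −9 |

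The sign depends on Se and Sp, and at high true uptake even modest forgetting outweighs over-claiming. Setting Se = 1 gives p + (1 − p)f, where f = 1 − Sp. That version cannot fall below p, so it cannot be used to show that the error is upwards.

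**3. What does a missing interview cost?**

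Selection of Subjects allows up to 60 women and the allocation ratio is not stated. Assuming 1:1, the intervention arm has at most 60 / 2 = 30 women, and each missing interview removes 1/30 = 3.3 percentage points of the denominator. Three missing interviews would leave 3/30 = 10 points undetermined. Post-test completion has no such gap: it can be tabulated for every woman randomised to the intervention, and an absent post-test counts as not completed.

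**The case against.** The strongest reply is that the text never says chapter completion will be recalled, or that the interviewer will work without records. Chapter tests are collected anyway, so a skipped chapter is not hidden from the team. For the employer letter the woman is the natural source, and for the texts no better one is described. The item is descriptive, in a small pilot, and enters no success rule.

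Most of this stands, and it limits the point to chapters. It does not remove it. The analysis section names the interview and nothing else, and nowhere ties the chapter tests to adherence. Leaving the link unstated invites two different uptake figures, and leaves women without an interview out of the one that the plan specifies.

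A reader might go further and infer that reported uptake is inflated, and that existing records could remove the error. The documents support neither. They contain no recall data, and part 2 of the working shows that the error can go either way. The post-tests address chapters only.

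A reader might also want to count text sends and letter issue dates as adherence. That would credit a woman who ignored every text, and would duplicate the separate delivery criterion under another name.

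**Conclusion.** The point holds for the presentation chapters. The plan takes a listed acceptability measure from self-report alone when a contemporaneous record of chapter completion is already planned and would cover women who are not interviewed.

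The size of any misreporting cannot be derived from the documents. The assumed values tabulated above give errors from −12 to +20 points, which shows only that the sign is open. The loss of about 3 points of denominator per missing interview rests on an assumed 1:1 allocation and full recruitment of 60.

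The conclusion also relies on the post-test following the chapter, as Design & Procedures says. A completed post-test shows that the chapter was reached, not that it was watched attentively.

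The consequence is moderate. The adherence item has no threshold, and the top-rating criterion does not use it, so no success decision changes. The gain is a sounder and more complete description of uptake.

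**What to change.** Add a short paragraph to Data Analysis & Statistical Considerations:

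- **Chapters.** Define adherence as post-test completed for each chapter relevant to the woman's IP3. Report it by chapter, with all women randomised to the intervention whose IP3 includes that chapter as the denominator, whether or not they were interviewed. Show any recalled value beside it.
- **Texts read and employer letter used.** Keep these as exit-interview items, label them as self-report, and state how many women were interviewed.
- **Texts sent and letters issued.** Report these under the delivery (feasibility) criterion, not as adherence.

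Also align the IP3 Knowledge item, which loosely places both tests before each chapter, with Design & Procedures, which places the post-test after it.

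The cost is one paragraph and a small export of test completions, with no new contact with participants. The downside is that the uptake figure may be less favourable. The definition should be settled before data are summarised.

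### Is the over-80% acceptability rule unusable because it does not say which arm's ratings it counts?

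*Combined protocol and SAP*

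**What the plan says.** Purpose of the Study makes acceptability one of two hypotheses, met if "over 80% of participants give the intervention top rating in their exit interview". Data Analysis & Statistical Considerations repeats the threshold. It opens the topic with "Acceptability will be measured by an exit interview which includes" and lists three items: a quantitative look at how well the intervention's parts were followed, qualitative suggestions for altering it, and "participants overall rating of the intervention over 80% of participants give the intervention top rating in their exit interview". No arm is named, and nothing is said about women who have no exit interview.

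The word for the raters is used in two ways in Design & Procedures. It covers everyone in "We will use redcap to randomize participants to the intervention or an active control", and only the intervention arm in "Participants will view the chapters of the presentation that are relevant to their specific IP3". The control arm has its own content, including "A narrated powerpoint with general information about the Duke Prematurity Prevention Program". The only exit-interview question described there concerns the employer letter, an intervention-arm item: staff will "ask if patients actually used it and found it helpful during the exit interview".

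Background & Significance says the study will "test the intervention via a pilot randomized controlled trial comparing our intervention to an active control". Selection of Subjects caps recruitment at 60. The allocation ratio is not stated.

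**The concern.** The rule gives a pass or fail verdict on a stated hypothesis, so its denominator ought to be fixed before ratings are seen. Taken word by word, it could be read over both arms, and the two readings can then disagree. Suppose there are 30 women per arm and controls rate their own materials. Then 27/30 top ratings in the intervention arm and 21/30 in the control arm pass on the intervention arm alone (90%) but fail pooled (48/60 = 80.0%, which is not over 80%). With 24/30 and 25/30 the verdicts reverse (80.0% fails; 49/60 = 81.7% passes). If the wording really left that choice open, the verdict could be picked afterwards.

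A second worry follows from the same silence. A trial described as a comparison with an active control sets out no between-arm analysis, so the control arm can look as if it serves no purpose.

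**Working it through.** The documents give no sample-size, power or precision figure for this criterion, so there is nothing of the plan's own to reproduce.

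**Inputs.** Threshold: strictly more than 80% (Purpose of the Study; Data Analysis & Statistical Considerations). Maximum enrolment: 60 (Selection of Subjects). Assumed: full enrolment and 1:1 allocation, so 30 per arm; 2:1 (40 and 20) is shown as a range. Assumed for illustration: 26 of 30 intervention women interviewed.

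**Step 1: which arm?** Three readings are conceivable.

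- *All 60 count, and controls cannot rate an intervention they did not receive.* The best possible result is 30/60 = 50% (2:1: 40/60 = 66.7%). The hypothesis could never be met, so this is not a credible meaning.
- *All 60 count, and controls rate their own materials.* The documents nowhere say that controls rate their materials, and the criterion counts ratings of the intervention. The opposite verdicts shown above depend on this unsupported reading.
- *Intervention arm only.* This fits the object of the rating, all three exit-interview items and the employer-letter question. The 95% delivery criterion likewise concerns the intervention's components.

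The double use of the word for participants does not upset this. In Design & Procedures its scope follows the subject of the sentence: everyone when randomisation is described, one arm when that arm's content is described. In the acceptability rule the subject is the intervention.

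**Step 2: pass mark in the intervention arm.** The smallest passing count is floor(0.8n) + 1.

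| Denominator n | Pass mark | Percentage |
|---|---|---|
| 20 | 17 | 85.0% |
| 26 | 21 | 80.8% |
| 30 | 25 | 83.3% |
| 40 | 33 | 82.5% |

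At 25/30 the exact (Clopper-Pearson) 95% interval is 65.3% to 94.4%, and one woman moves the result by 1/30 = 3.3 points.

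**Step 3: interviewed or randomised?** With 26 of 30 interviewed, 22 top ratings are 22/26 = 84.6% (pass) or 22/30 = 73.3% (fail). The two denominators disagree for any count from 21 (the pass mark at n = 26) to 24 (one below the pass mark at n = 30). If all 30 are interviewed they coincide. If 29 are, the pass mark is floor(23.2) + 1 = 24, and they disagree only at exactly 24 (24/29 = 82.8%; 24/30 = 80.0%). The ambiguity therefore grows with the number of missing interviews and vanishes without them.

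**The case for a change.** The strongest case for a change concerns the denominator within the intervention arm. Follow-up runs to postpartum, so some exit interviews may well be missed. If 26 of 30 women are interviewed and the true top-rating rate among them is 90%, the chance of passing is 0.96 with interviewed women as denominator. With all randomised women it is the chance of at least 25 top ratings out of 26: 26 × 0.9^25 × 0.1 + 0.9^26 = 0.187 + 0.065 = 0.25. That is a large gap, the documents do not settle it, and women who skip the interview may be the less satisfied ones. One sentence would close it.

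The arithmetic stands, and so does the observation that the text is silent. What does not follow is that the plan would lead an analyst astray. Both statements of the criterion tie the rating to the exit interview, and a woman without an interview has given no rating. Counting her as not giving a top rating turns the rule into a joint test of acceptability and retention, which the plan does not describe. An analyst would use interviewed women and report how many were not interviewed; the other percentage can be worked out from those two counts.

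On the control arm, the absence of a planned between-arm test is real, but the arm is not without a role. Background & Significance makes it the comparator. Women consent before allocation, so the enrolment target necessarily counts both arms. The study calls itself a feasibility and acceptability pilot, and leaving out an efficacy comparison at this size is a defensible choice.

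**Conclusion.** The concern does not call for a change. That no arm is named is literally true, but what is rated and what the exit interview covers identify the raters as intervention-arm women. The reading that would make the rule impossible (a 50% ceiling) can be discarded for that reason, and the pooled reading has no support in the documents. What is left is a gap in detail: interviewed versus all randomised women in that arm. It affects the verdict only when interviews are missing and the count falls in a limited band, 21 to 24 top ratings in the illustrated case of 26 interviewed out of 30. The sensible default is clear, and plain reporting of the counts covers the alternative. These sizes assume 60 enrolled and 1:1 allocation, neither of which is guaranteed, and the number interviewed is illustrative. In a pilot where even a bare pass at 25/30 leaves an interval from 65.3% to 94.4%, the result will be read as descriptive whichever denominator heads the report.

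### The one acceptability criterion with a pass mark is collected in an exit interview whose interviewer and mode are not stated; a private, self-completed rating would remove a possible upward bias cheaply

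*Combined protocol and SAP*

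**What the plan says.** The Purpose of the Study section sets the hypothesis that the intervention is "acceptable (over 80% of participants give the intervention top rating in their exit interview". The Data Analysis & Statistical Considerations section says how this will be assessed: "Acceptability will be measured by an exit interview which includes" three things. The first is a "quantitative assessment of the adherence to intervention components". The second is "qualitative feedback about how the intervention should be changed". The third is the overall rating, given as "participants overall rating of the intervention over 80% of participants give the intervention top rating in their exit interview". The first two have no success criterion, so the rating alone settles whether the intervention is called acceptable.

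Design & Procedures adds another topic to the same interview. For the employer letter, the team will "ask if patients actually used it and found it helpful during the exit interview". That section also shows that the study already has an electronic route for data ("Once consented, patients will complete an intake via a red-cap data base") and that women in both arms receive regular text messages.

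No section says who conducts the exit interview, in what setting or by what mode, what rating scale is used, or whether the rating is kept from the woman's clinicians.

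**The concern.** Women are recruited from the clinics where they receive care, and one intervention component is a letter of encouragement from the provider. A woman asked for an overall rating by someone connected with the study or clinic may give a kinder answer than she would in private, especially in a conversation that also covers how well she kept to the components. If that happens, the top-rating share goes up, and the pass rule counts nothing else. An intervention that would miss the bar on private ratings could then be declared acceptable.

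The number of raters is small, so a few changed answers can decide the result. The plan describes nothing that would limit this, such as self-completion, an interviewer independent of the clinic, or an assurance of confidentiality.

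**Working it through.** The plan has no figure to reproduce here: it states no expected rating rate, error rate, power or dropout. What follows is an illustration under stated assumptions.

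**Inputs from the documents**
- Pass rule: more than 80% top ratings (Purpose of the Study; Data Analysis & Statistical Considerations).
- Sample: "We will recruit up to 60 pregnant women from the Duke Perinatal Clinics" (Selection of Subjects), randomized to two arms in an unstated ratio.

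**Assumptions, not in the documents**
- 1:1 allocation and every intervention participant rating, so n = 60 / 2 = 30.
- Private top-rating rate p of 70% or 75%.
- A share s of the women who would privately withhold the top rating give it when asked in the interview.

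**Step 1. Count needed.** 0.80 × 30 = 24. The rule is strictly more than 80%, so at least 25 of 30 are needed (83.3%).

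**Step 2. Observed rate.** q = p + s(1 − p). For p = 0.70 and s = 0.10, q = 0.70 + 0.10 × 0.30 = 0.73.

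**Step 3. Chance of passing.** P(X ≥ 25), where X is binomial with n = 30 and probability q.

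| Private rate p | Switching share s | Observed rate q | Chance of passing |
|---|---|---|---|
| 70% | 0 | 0.70 | 0.077 |
| 70% | 10% | 0.73 | 0.141 |
| 70% | 20% | 0.76 | 0.240 |
| 70% | 30% | 0.79 | 0.375 |
| 75% | 0 | 0.75 | 0.203 |
| 75% | 10% | 0.775 | 0.303 |
| 75% | 20% | 0.80 | 0.428 |
| 75% | 30% | 0.825 | 0.568 |

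The rows with s = 0 correspond to a private rating free of courtesy bias.

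**Step 4. Sensitivity to the number of raters.** If all 60 women rated, 0.80 × 60 = 48, so at least 49 are needed. From p = 70%, the chance of passing goes from 0.029 (s = 0) to 0.082, 0.192 and 0.374 for s = 10%, 20% and 30%. With fewer raters and no bias, the chance at 70% is 0.107 for n = 20 (17 needed) and 0.090 for n = 25 (21 needed), close to the 0.077 for n = 30.

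**Step 5. How large a lift is plausible.** A lift in percentage points implies a switching share of lift / (1 − p). From 70%, lifts of 10, 15 and 20 points require 10/30 = 33%, 15/30 = 50% and 20/30 = 67% of the non-top raters to switch. Under such lifts the chance of passing would be 0.428, 0.711 or 0.927, but they are large shifts, and nothing in the documents supports them over smaller ones.

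**The case against.** The strongest reply is that the plan is silent on mode and does not choose a spoken rating. A reader might infer that the rating is given aloud to staff, but the documents do not say so. They also use the word interview loosely: Design & Procedures has the woman complete the intake in REDCap, and the Measures list then calls the intake an interview. An exit interview could likewise include items she enters herself. The sentence in which the team asks about the employer letter makes a conversation likely, but it concerns the letter and not the rating. This part of the objection stands.

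It is also fair to say that the documents do not show courtesy bias to be present, and that the rating scale is not described. The interview openly invites suggestions for change, which may ease criticism. Nor does anything suggest that providers are shown the ratings. The point therefore concerns a risk and its direction; it does not establish a bias.

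Finally, self-completion can cost responses. If, say, 3 of 30 ratings were missing and 22 were top, the result would be 22/27 = 81.5% among responders (a pass) but 22/30 = 73.3% with missing counted as not top (a fail). This is a real cost for an item sent only as a text link. It is much smaller if the item is completed on a device at the exit contact, when the woman is already present.

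What the objection does not remove is that the only item with a pass mark sits in this interview and that no safeguard is described.

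**Conclusion.** The point holds as a conditional one. The deciding acceptability rating is collected in an exit interview whose interviewer and mode are unstated. If staff ask for it directly, courtesy could inflate the top-rating share, and that would favour passing. With 30 raters and a private rate of 70%, switching by 10% to 30% of non-top raters would raise the chance of passing from 0.08 to between 0.14 and 0.38. From 75%, it would go from 0.20 to between 0.30 and 0.57. These figures rest on assumed 1:1 allocation, complete ratings, and assumed private rates and switching shares.

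Two stronger readings should not be drawn. The documents do not establish that the rating is spoken, and they do not show that a bias exists or is large enough to turn a probable failure into a near-certain pass. No sample-size or error-rate figure in the plan depends on this point. It is an inexpensive improvement that protects one of the pilot's two conclusions.

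**What to change.** In Purpose of the Study and in Data Analysis & Statistical Considerations:

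- Define the overall rating as a self-completed REDCap item, answered privately on a device at the exit contact before any interview question is asked, with a text link as back-up.
- Apply the over-80% rule to that item.
- Tell participants that their provider will not see individual ratings.
- Report the number of missing ratings alongside the result.
- State who conducts the exit interview, and keep it for the qualitative feedback and the questions on components and the employer letter.

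If a private rating is already intended, a sentence saying so closes most of the gap. The cost is one REDCap item and a wording change; REDCap and text messaging are already in use, and no extra visit is needed. The downside is that a few ratings may be missing and the measured top-rating rate may be somewhat lower.
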